5.11 Secondary Outcome Analyses

5.11.1 Secondary Hypotheses

5.11.1.1 Secondary Hypothesis 1

We hypothesize that perceived stress (PSS-14) will decrease by a Cohen's $d = 0.50$ more in the Tertulias arm over this time period than in the control arm.

5.11.1.2 Secondary Hypothesis 2

We hypothesize that, compared to participants in the control arm, those in the Tertulias arm will increase their social connectedness as assessed by Social Network Analysis.

5.11.2 Secondary Analysis

Analyses for the PSS outcome will mirror those described in the Primary Analysis section (5.10.2); however, 95% confidence intervals will be reported instead.

The TIPS subscales will be summarized with descriptive statistics, with means and 95% confidence intervals reported. This data is only collected in the Tertulias arm at 12 months.

Social Network Analysis (SNA) will include analyses of the networks of support surrounding respondents in their daily lives as well as analyses of the networks that grow within the Tertulias groups. Information about support in their daily lives will be classic egocentric network data, and will include who they can turn to for help with personal problems, for transportation to doctor visits if needed, for information about resources and assistance, and who they have fun with. Further information collected about these people (the respondents alters) include their age, education, ethnicity, their relationship to the respondent, how they met, and how often they interact, how close the respondent feels to them, and how close the respondents' connections are to each other. Ego network analyses will examine changes in the size, closeness, network overlap (transitivity) and composition of respondents' daily life networks over the course of the study, and how these relate to other well-being measures. The information on relationships within the Tertulias groups will be complete network data

(sociocentric), using the survey responses of all participants in each group. Respondents are asked about types of support received from each co-member of their group. Tertulias network analyses will examine changes in the density, segregation, and inequality in the ties of support between the members across the study. We will also examine the correlates of connections (who becomes connected to whom) and how relationships in the group are related to engagement with the project and well-being outcomes. Network analytic strategies will include visualization, descriptive measures, and inferential models.

5.12 Exploratory Outcome Analyses

Cortisol levels will be compared to the established averages and determined to be within normal limits or not. Pregnancy (determined by a question on the survey) will be considered in our analysis. Summary measures (means or medians and corresponding 95% CIs, as appropriate) will be computed for hair cortisol measures at each time point and the mean changes and 95% CIs over time in each arm will be compared between arms. Correlational analysis will be performed to understand how hair cortisol levels, as a marker for stress, is related to our primary and secondary outcome measures.

5.13 Sub-Group Analyses

We will conduct exploratory analyses to see if patient sex or gender, or race/ethnicity has an effect on primary outcomes or retention. Adjusted odds ratios and their 95% confidence intervals will be calculated from interaction effects between treatment group and sex or gender from the specified linear models for the primary and secondary outcome measures.

5.14 Post-Hoc Analyses

The Tertulias leadership team will encourage collaboration across all sites and investigators and provide guidance to promote and support scientific research dissemination. Research “ideas” for abstracts, manuscripts and presentation will be generated on “Concept Sheets” and submitted for review to the Tertulias Leadership group. Concept sheets will each have detailed analysis plans for the proposed study question/s. All papers will include a biostatistician in the collaborative/authorship group. In general, we expect both descriptive and comparative analyses will be conducted on cross-sectional and longitudinal data collected in the Tertulias study.

5.15 Safety Analyses

All adverse events (AEs) will be categorized and graded for severity as described above. (S)AEs will be summarized via the methods described in section 5.9, by site and overall. SAEs will be individually listed for DSMB review and will also be categorized and summarized similarly to AEs. We report AEs and SAEs by number of events (# AEs may be $> N$), as well as by the subject’s most severe AE and its severity (#AEs $\leq N$). These analyses will be performed on the ITT population defined in Section 5.2.1.

5.15.1 Adverse Events

The Tertulias protocol defines an adverse event (AE) as any unfavorable and unintended symptom or disease that an investigator or study staff learns about which occurs during a participant’s enrollment in the study, if it is considered by the site study team to be possibly related to a study treatment or procedure (“possibly related” means there is a reasonable possibility that AE may have been caused by research procedures).

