### Responsible Party for Monitoring

The PI will be the ultimate individual responsible for monitoring risk, but facilitators and data collectors who interface with participants will have training and protocols in place in the event that they encounter a data or safety issue.

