3.2 Intervention Arms

3.2.1 Arm 1: Control

Using a modified Attention Control Placebo (ACP) design to reduce attrition over the 12 months, control arm participants will receive a bimonthly phone call from our project coordinator to check in with them, make sure their contact information is correct, and let them know that the study is continuing.

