3.2.2 Arm 2: Intervention

We will conduct Tertulias structured dialogue groups using the model we developed and tested through our preliminary research (see [name] et al. 2021).⁹ Each group will have approximately 10 women and will meet weekly for 2 hours over a 12-month period. Group meetings will be conducted in Spanish, led by a team of two FMI facilitators using our structured dialogue approach. Because of required safety restrictions related to the COVID-19 pandemic, our original intention to hold these groups in-person was amended to hold the groups remotely by Zoom. We will work further with each Arm 2 participant to ensure that they know how to use Zoom and have electronic access.

[figure not shown]

Figure 1. CONSORT diagram for the Tertulias study.

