5.15.2 Serious Adverse Events

5.15.2.1 Definition of SAE

The Tertulias protocol defines a serious adverse event (SAE) as an AE that an investigator or study staff learns about that is fatal, life-threatening, requires inpatient rehospitalization, or is medically significant and which the investigators and/or clinicians regard as serious based on appropriate medical judgment. With the exception of fatalities, other SAEs documented in this study are considered those possibly related to the study.

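### Adverse events are recorded only if staff learn of them, and staff contact differs widely by arm, so by-arm adverse-event counts are open to ascertainment bias of unknown size

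*SAP*

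**What the plan says.** **Definition.** SAP 5.15.1 defines an adverse event as "any unfavorable and unintended symptom or disease that an investigator or study staff learns about" during enrolment, and counts it only "if it is considered by the site study team to be possibly related to a study treatment or procedure". SAP 5.15.2.1 carries the same passive rule into serious events, defining one "as an AE that an investigator or study staff learns about that is fatal, life-threatening" or meeting other listed criteria. Fatalities are the only serious events exempt from the relatedness condition.

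**Contact.** In Arm 1, "control arm participants will receive a bimonthly phone call from our project coordinator" (SAP 3.2.1). In Arm 2, each group "will meet weekly for 2 hours over a 12-month period" (SAP 3.2.2). Protocol 9.0 adds WhatsApp chat groups for Arm 2, whose streams the team reviews as qualitative data.

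**Common assessments.** SAP 3.5.2 and Protocol 9.0 list the baseline and 12-month content asked of both arms: the scales, social-network questions, demographics and hair samples. No adverse-event question is among them.

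**Reporting.** SAP 5.15 says events will be "summarized via the methods described in section 5.9, by site and overall", on the ITT population. SAP 5.9 is the baseline section; it compares the intervention arms descriptively on the Table 2 variables. SAP 3.4.2 calls the study unblinded. Protocol 8.0 names no safety endpoint.

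**Oversight.** SAP 5.15 states that "SAEs will be individually listed for DSMB review". Protocol 11.0 states that "The PI will be the ultimate individual responsible for monitoring risk" and sends adverse events to the university's human research protections office (HRPO).

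**The concern.** When an event counts only if staff hear of it, the count reflects both how often events happen and how often staff are in a position to hear. Here the second factor differs between arms by design. Facilitators see Arm 2 every week in sessions meant to encourage disclosure. The project coordinator telephones Arm 1 mainly to check in, confirm contact details and say that the study continues.

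The relatedness condition could add to the imbalance. Unblinded staff decide whether an event is possibly related to a study treatment or procedure, and a control participant has few procedures to which an event could be attributed.

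The SAP commits to reporting adverse and serious adverse events. A reader who sees more of them in Arm 2 could infer harm from the groups, and a low count in Arm 1 could be taken as reassurance. Either impression could come from contact frequency alone.

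**Working it through.** The plan states no adverse-event rate, detection rate or safety sample size, so there is no figure of its own to reproduce. The check counts contacts and then shows what unequal contact could do.

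**Step 1: scheduled contacts per year.** Arm 2: one session a week, about 52. Arm 1: 6 if bimonthly means every two months, 24 if it means twice a month. The documents do not say which. Ratios: 52/6 = 8.7 and 52/24 = 2.2.

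**Step 2: illustration with equal true risk.** Assume each contact has the same chance q of bringing an event to light, independently. The chance that staff learn of it over k contacts is 1 − (1 − q)^k. The value of q, and its being equal for a group session and a call, are assumptions.

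| q | Arm 2, k = 52 | Arm 1, k = 6 | Apparent RR | Arm 1, k = 24 | Apparent RR |
|---|---|---|---|---|---|
| 0.01 | 41% | 6% | 7.0 | 21% | 1.9 |
| 0.02 | 65% | 11% | 5.7 | 38% | 1.7 |
| 0.05 | 93% | 26% | 3.5 | 71% | 1.3 |
| 0.10 | 100% | 47% | 2.1 | 92% | 1.1 |

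**Step 3: a second model.** Suppose an event can be disclosed only during the 8 weeks after it happens. That window holds 8 Arm 2 sessions against 1 call (every two months) or 4 calls (twice a month). For q from 0.05 to 0.40, the apparent ratio is 6.7 down to 2.5 with 1 call, and 1.8 down to 1.1 with 4.

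In counts, take 126 per arm (Protocol 4.0), an assumed true risk of 20% in both arms and q = 0.2:
- Arm 2: 126 × 0.20 × (1 − 0.8^8) = 21 recorded events.
- Arm 1, 1 call: 126 × 0.20 × 0.2 = 5.
- Arm 1, 4 calls: 126 × 0.20 × (1 − 0.8^4) = 15.

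**Step 4: relaxing the equal-chance assumption.** An individual call may draw out more than a group session of about ten women. With an assumed 5% per session and 20% per call, Arm 2 detection is 1 − 0.95^52 = 93%. Arm 1 detection is 1 − 0.8^6 = 74% with six calls, a ratio of 1.26. With 24 calls it is 1 − 0.8^24 = 99.5%, and the ratio falls to 0.931/0.995 = 0.94. So neither the size nor, in the extreme, the direction is fixed by the documents.

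**Step 5: reach of a new question.** The SAP is dated June 23, 2024. Protocol 9.0 places the last cohort's follow-up in July/August 2024. That cohort is 66 of 252 participants under Protocol 4.0: 66/252 = 26%, before attrition.

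**The case against.** **No formal safety comparison is planned.** This stands. Protocol 8.0 names no safety endpoint, and SAP 5.15 plans descriptive summaries and listings. The events are also limited to those judged possibly related, a filter that the arithmetic above ignores. The most that can be said is that a by-arm reading of the counts is open to bias.

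**The magnitudes are assumed.** This stands too, as Step 4 shows. No single ratio should be relied on.

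**A reader might infer that the tables will omit arm.** The documents do not establish that. SAP 5.15 refers to 5.9, which does compare arms. But 5.9 concerns baseline characteristics, so a by-arm safety table has to be inferred.

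**A reader might infer that worsening depression in controls would go unseen.** It would not. The CES-D and PSS are given to both arms at baseline and 12 months, and CES-D change is a primary outcome. Protocol 9.0 also describes help for any participant, control or intervention, identified as needing immediate medical or counseling services. Such worsening might simply not be recorded as an adverse event.

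**Some absences cannot be fully checked.** The survey attachments are not available. Protocol 27.0 shows that the data include health status, medication use and sleep quality, which SAP 3.5.2 does not itemize. The missing adverse-event question is therefore a statement about the listed assessments only. Parts of the protocol were also not available, so the oversight mismatch holds for the readable text and does not show that no DSMB exists. It is a separate governance point and not evidence of biased capture.

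**Conclusion.** The point holds in a limited form. Passive capture, an unblinded relatedness filter (deaths apart), unequal scheduled contact and no listed common adverse-event question together leave any by-arm comparison of event counts open to differential ascertainment. More recorded events in Arm 2 is the likely direction. It holds wherever a session and a call are assumed equally likely to surface an event, and it can weaken or reverse if calls are much more productive and come twice a month. Under the equal-chance assumption the illustrative apparent risk ratio is about 7 to 2.1 with 6 calls and 1.9 to 1.1 with 24. The true size is unknown.

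The efficacy analyses are not affected. What is at risk is the interpretation of the safety tables.

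**What to change.** 1. In SAP 5.15, state that adverse and serious adverse events are tabulated by arm as well as by site and overall, without relying on the reference to 5.9.
2. At the remaining 12-month interviews, ask both arms one identical structured question (for example hospital stay, emergency visit or serious worsening of health since baseline). Record the answer whether or not the event is judged related. Report it by arm as solicited data for that cohort only; it cannot carry the comparison for the whole trial.
3. List unsolicited events separately by arm, with the number of staff contacts and how each event came to light. State that these counts do not support a comparison between arms.
4. Define bimonthly as a number of calls per year.
5. Reconcile the SAP's DSMB review with the protocol's PI and HRPO statements, so that it is clear who receives the serious-event listings.

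Items 1, 3, 4 and 5 are mainly changes of wording and reporting, though item 3 depends on contact records and the source of each event being available. Item 2 needs one survey item and a minor amendment, approved in time for the July/August 2024 interviews. It reaches at most about a quarter of participants. The earlier cohorts, about three quarters of the trial, will have only unsolicited reports whatever is done now.

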■) **Additional Survey Questions**. At the end of Y2, we conducted a preliminary analysis of the data. Qualitative data were extremely powerful regarding participant self-report about the importance of the intervention and the deep significance it has had on them as individuals and in their lives. These findings are clear in the data from meeting notes, interviews, evaluation discussions, and Ripple Effects Mapping sessions, and are supported by perceptions of team members who facilitate the peer support groups. However, when we analyzed the pre/post survey data using quantitative methods, there was little or no difference between the arms. It didn't seem possible that being in such an intensive intervention with reports from the participants of such deep impact could be the same as receiving nothing. So the results were not only surprising to us, they don't make sense. After much discussion with team members, our Advisory Board, individuals from the population of study, and experts in research methods, and reviewing the literature, we hypothesize that the discrepancy and lack of alignment between our qualitative and quantitative data may reflect the following: 1.) There may be some impact from the pandemic which was universally affecting participants from both arms of the study, 2.) Although the survey is conducted by 2 female Mexican immigrant data collectors, the participants do not know the data collectors—they are strangers—and this makes disclosing truthful answers to questions about mental and behavioral health (the focus of this study) challenging. There is much published data regarding the fact that in Mexican culture, people tend not to want to disclose information about mental and behavioral health (the focus of this study), and that this is particularly true for Mexican women. 3.) There is a lot of shame associated with mental and behavioral health issues in Mexican culture. 4.) Many people from the population of study do not really understand what

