3.4.2 Blinding

This is an unblinded study. Research staff will only have access to blinded reports with treatment groups indicated by "Arm A" and "Arm B" until the final analysis is performed.

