5.15.3 Relationship to Study Intervention and Severity of (S)AEs

All (S)AEs will be rated as Mild, Moderate, or Severe and will be used as a factor in determining expectedness of an event. All (serious) adverse events will have their relationships to the study intervention assessed and rated as either Definitely Related, Probably Related, Unlikely to be Related, or Not related.

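### Non-fatal adverse events are counted only if staff in an open-label trial judge them possibly related, and the rating scale has no possibly-related level

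*SAP*

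**What the plan says.** SAP 5.15.1 makes relatedness part of the definition. An unfavourable event that staff learn of during enrolment is an adverse event (AE) only "if it is considered by the site study team to be possibly related to a study treatment or procedure". The same sentence explains that possibly related "means there is a reasonable possibility that AE may have been caused by research procedures".

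SAP 5.15.2.1 defines a serious adverse event (SAE) as an AE meeting certain criteria, then adds: "With the exception of fatalities, other SAEs documented in this study are considered those possibly related to the study".

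SAP 5.15.3 applies a relatedness rating to every AE and SAE, taken against the study intervention. Each event is to be "rated as either Definitely Related, Probably Related, Unlikely to be Related, or Not related".

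SAP 5.15 summarises the resulting events per site and in total, by number of events and by each participant's most severe event. It refers to the methods of SAP 5.9, which compares the arms descriptively, and it sends the SAE listings to a DSMB.

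On masking, SAP 3.4.2 states "This is an unblinded study", and adds "Research staff will only have access to blinded reports with treatment groups indicated by" coded arm labels until the final analysis. Protocol 8.0 names no safety endpoint. Protocol 11.0 gives a reporting route for adverse events but, in the text available, no definition and no relatedness scale.

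**The concern.** Relatedness does two jobs in this plan, and the two do not fit together. It is the entry condition for the event log, at the threshold of possibly related. It is then a rating, on a scale that omits that threshold. An event admitted on the weakest qualifying ground has no code that describes it.

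The entry condition also matters in itself. A non-fatal event that staff judge unrelated is never an AE, so no later tabulation can recover it. The judgement is assigned to the site team of an open-label trial, and that team has far more contact with one arm than with the other. At stake is whether the safety tables can support any statement about how often harms occurred or whether they differed between arms.

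**Working it through.** No sample size, power or event figure is involved, so the check sets the rules side by side and follows each kind of event through them.

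| Event | Admitted by 5.15.1 / 5.15.2.1? | Code in 5.15.3 |
|---|---|---|
| Non-fatal, probably or definitely related to the intervention | Yes | Fits |
| Non-fatal, only possibly related to the intervention | Yes | None. Probably overstates it; Unlikely undercuts the reason it was admitted |
| Non-fatal, possibly related to a survey, hair sample or visit, but not to the groups | Yes | Unlikely or Not related fits, if intervention means the groups only |
| Non-fatal, judged unrelated to anything in the study | No | Never rated |
| Fatal, judged unrelated | No under 5.15.1; yes under 5.15.2.1 | Not related fits, but the event is not an AE |

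Four things follow.

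1. **Missing level.** The second row has no correct code. Whichever way it is pushed, the record misstates the judgement that admitted the event.
2. **Shifting referent.** SAP 5.15.1 asks about a treatment or procedure, SAP 5.15.2.1 about the study, and SAP 5.15.3 about the intervention. The third row can be coded only because of that shift, which the SAP does not explain.
3. **Deaths.** An SAE must be an AE, and an AE must be possibly related. The exemption nonetheless keeps unrelated deaths. Both rules cannot hold as written.
4. **Order of operations.** SAP 5.15 tabulates only events that have passed the filter. The SAE listings for the DSMB are filtered in the same way, apart from deaths.

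Next, the opportunity to learn of events. SAP 3.2.2 gives the intervention arm a weekly two-hour group for 12 months. SAP 3.2.1 gives controls a bimonthly call. Assume a group every week, with every session attended and every call completed:

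- Intervention: 52 weeks × 1 = 52 sessions, or 52 × 2 = 104 hours.
- Control, if bimonthly means every two months: 12 ÷ 2 = 6 calls. Contact ratio 52 ÷ 6 ≈ 8.7.
- Control, if bimonthly means twice a month: 12 × 2 = 24 calls. Contact ratio 52 ÷ 24 ≈ 2.2.

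On either reading staff have more occasions to hear of an event in the intervention arm. These are ratios of contacts and do not estimate bias in event counts. Controls also undergo fewer activities to which an event could be attributed.

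**The case against.** The strongest reply is that logging only possibly related events is a defensible choice in a behavioural trial with no safety endpoint, and that SAP 5.15 plans no formal safety test between arms. That stands as far as it goes. But the SAP does commit to safety summaries using methods that compare arms, so the reader must be told what those summaries contain.

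Several stronger readings are tempting, and the documents do not support them.

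- *Two of the four codes can never be used for non-fatal events.* This would follow only if the sections shared one referent. An event tied to a survey, hair sample or appointment can meet SAP 5.15.1 and still be properly coded as unrelated to the intervention.
- *The AE tables contradict themselves.* SAP 5.15 does not name relatedness as a table dimension. The inconsistency lies in the definition and rating rules, and the tables inherit it through which events enter.
- *The control arm must show almost no events.* Controls also have surveys, hair samples and appointments. Protocol 14.0 names loss of confidentiality as a risk in both arms, and Protocol 12.0 lists COVID-19 exposure at data collection.
- *Most events are lost.* No figure in the documents supports any share.
- *Staff belief in the programme biased the coding.* Protocol 9.0, comparing the programme with no intervention in the light of the interim survey results, says "It didn't seem possible that being in such an intensive intervention with reports from the participants of such deep impact could be the same". That concerns efficacy data and does not show that any event was misjudged. Nor does the SAP say whether the person judging relatedness is masked. Knowledge of arm is inferred from the open-label design.

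It is also fair to say that worsening depression is not invisible, since the CES-D is collected in both arms at baseline and 12 months. Protocol 9.0 also provides help for any participant, in either arm, found to need immediate services. A participant could, however, use that help and not appear in an AE table if staff judged the event unrelated.

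**Conclusion.** The point holds. SAP 5.15.1, 5.15.2.1 and 5.15.3 cannot all be applied as written. An event only possibly related to the intervention has no correct code, the referent changes between sections, and unrelated deaths are both excluded and kept. Because the filter precedes tabulation and contact differs by arm, the counts can be biased by arm and are not harm rates.

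The size in events is unknown. The direction is also unsettled: less contact and fewer activities would tend to lower control counts, while reluctance to attribute harm to the groups would lower intervention counts.

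The conclusion rests on the SAP wording and on the inference that the site team knows the arm. The SAP credits its definitions to the protocol. The protocol text available contains none, but some pages were withheld, so this cannot be counted as an omission. The three primary outcomes are not affected. The rules should be corrected before the safety tables are produced.

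**What to change.** 1. In SAP 5.15.3, add a Possibly Related level and use one referent in all three sections. The broader one (any study treatment or procedure) would cover both arms.
2. Reconcile SAP 5.15.1, 5.15.2.1 and 5.15.3 so that relatedness is an attribute recorded for every unfavourable event that was logged, serious or not, and is no longer an entry condition. This also removes the conflict over deaths. Check the result against the protocol definition that the SAP cites.
3. Re-rate events already coded on the four-level scale, if possible by someone not told the arm.
4. In SAP 5.15, tabulate all logged events by arm first, then the related subset.
5. Where unrelated events were not logged, state in the report that the tables hold only events staff judged possibly related, plus deaths; that ascertainment differed by arm; and that no between-arm safety conclusion is drawn.

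The last item is likely to matter most. The SAP is dated June 23, 2024, and Protocol 9.0 places the final cohort's follow-up in July/August 2024, so little prospective logging remained. The cost is some extra coding and tabulation, and a weaker safety statement.
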